STUDY PROTOCOL AND STATISTICAL ANALYSIS PLAN

Official Title:

**Effects of a Wearable Device and Social Media-Based
Intervention on Physical Activity and Sleep Quality in
Adults: A Randomized Controlled Trial**

NCT Number: NCT06739876

Organization Unique Protocol ID: NCUEREC-110-082

Document Date: August 15, 2025

1. Introduction and Objectives

The objective of this randomized controlled trial (RCT) is to evaluate the efficacy of a wearable device-based intervention, supplemented with social media support, on enhancing physical activity (PA) levels and improving sleep quality among adults. The study specifically investigates whether motivational support via social media (LINE) provides incremental benefits compared to using a wearable device alone.

2. Study Design and Setting

This study employs a three-arm, parallel-group randomized controlled trial design conducted at National Chung Hsing University, Taiwan. A total of 75 participants are randomly assigned to one of three groups in a 1:1:1 ratio.

Arm 1 (Device + Support): Garmin wearable device + motivational support via LINE.

Arm 2 (Device Only): Garmin wearable device only.

Arm 3 (Control Group): No intervention (standard lifestyle).

3. Eligibility Criteria

Inclusion: Healthy adults aged 18-64 who own a smartphone and have not previously used wearable fitness trackers.

Exclusion: Individuals with medical conditions that contraindicate increased physical activity or those currently participating in other PA-related interventions.

4. Detailed Intervention Protocol

Wearable Technology: Participants in Arm 1 and Arm 2 are provided with a Garmin activity tracker. They are instructed to use the "Move Alert" feature, which vibrates to prompt movement after periods of prolonged sitting.

Social Media Support (Arm 1 only): A structured LINE group is

established for:

Weekly Education: Sharing health knowledge regarding the benefits of sleep and PA.

Interactive Support: Research assistants provide tailored feedback via digital stickers and respond to participant inquiries.

5. Outcome Measures

Primary Outcome: Change in Physical Activity (measured by steps/day and sedentary breaks).

Secondary Outcome: Change in Sleep Quality (assessed via standardized sleep quality questionnaires and device-derived sleep metrics).

Assessment Points: Data are collected at Baseline (T0), Post-intervention (T1, 1 month), and Follow-up (T2, 2 months).

6. Statistical Analysis Plan (SAP)

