Data will be analyzed using SPSS software.

Descriptive Statistics: Baseline characteristics will be summarized as means (SD) or frequencies.

Main Analysis: A Two-way Mixed ANOVA (3 Groups \times 3 Time points) will be performed to examine the main effects of "Group" and "Time," as well as the Group-by-Time interaction effect on total sedentary time.

Post-hoc Testing: If a significant interaction is found, Bonferroni-adjusted post-hoc tests will be conducted to identify specific differences between groups at each time point.

Significance Level: The alpha level is set at 0.05.

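### The comparison Section 1 singles out (device plus LINE versus device alone) is tested only after a significant 4-df interaction and then with Bonferroni, at no named visit; a directly pre-specified contrast would fit the question better and cost less power

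*Combined protocol and SAP*

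**What the plan says.** Section 1 first states a broad aim, the efficacy of the device-based intervention with social media support, and then narrows it: "The study specifically investigates whether motivational support via social media (LINE) provides incremental benefits compared to using a wearable device alone". Section 2 gives the size: "A total of 75 participants are randomly assigned to one of three groups in a 1:1:1 ratio", so 25 per arm. Section 5 sets three assessments (T0, T1 at 1 month, T2 at 2 months).

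Section 6 names one main analysis, a 3 × 3 mixed ANOVA that includes the "Group-by-Time interaction effect on total sedentary time". Group comparisons come afterwards and are conditional: "If a significant interaction is found, Bonferroni-adjusted post-hoc tests will be conducted", with the purpose "to identify specific differences between groups at each time point". On level, it says only "The alpha level is set at 0.05".

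The plan does not name Arm 1 versus Arm 2 as a contrast in its own right, say which visit decides, or say whether Bonferroni covers 3 pairs per visit or all 9. It gives no effect size, SD, within-person correlation, power or sample-size rationale.

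**The concern.** The test that carries the analysis and the question that the study singles out are not the same. A 3 × 3 interaction responds to any departure from parallel profiles among three arms, including one produced wholly by device versus control. Two consequences follow from the structure alone:

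- A significant main analysis need not say anything about LINE.
- If the interaction misses, the plan gives no test of LINE at all, even when its effect is real.

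When the comparison is reached, it is tested at a reduced level that depends on an unstated divisor. With 25 per arm there is little power to give up. Because no visit is named, a difference at T1 only or at T2 only could each be read as the answer.

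**Working it through.** **Inputs from the documents.** 75 participants at 1:1:1, so n = 25 per arm (Section 2); 3 visits (Section 5); alpha 0.05, interaction precondition and Bonferroni (Section 6).

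**Assumptions, because the documents are silent.** Two-sided tests; SD 1; no dropout; equal correlation between visits, 0.3 to 0.7; LINE effect (Arm 1 minus Arm 2) d = 0.5 to 0.8 SD; device effect (Arm 2 minus Arm 3) 0 to 0.8 SD; arms equal at T0. There is no stated power figure to reproduce.

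**Step 1: the interaction test.** Numerator df = (3−1)(3−1) = 4. Error df = (75−3)(3−1) = 144.

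**Step 2: Bonferroni alone, normal approximation.** Power ≈ Φ(d√(n/2) − z), ignoring the negligible opposite tail, where z is the two-sided critical value and √(25/2) = 3.536. At d = 0.5 the shift is 1.768; at d = 0.8 it is 2.828.

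| Level | z | d = 0.5 | d = 0.8 |
|---|---|---|---|
| 0.05 | 1.960 | 0.42 | 0.81 |
| 0.05/3 | 2.394 | 0.27 | 0.67 |
| 0.05/9 | 2.773 | 0.16 | 0.52 |

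The undefined family therefore matters in itself.

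**Step 3: interaction precondition plus Bonferroni, by simulation.** For each simulated trial: compute the interaction F on 4 and 144 df; if it is significant, test Arm 1 versus Arm 2 at T1 with pooled SD at 0.05/3. The comparator is the same contrast tested directly at 0.05. Selected results (LINE effect equal at T1 and T2; 20,000 runs each):

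| d | Device vs control | Corr. | Interaction significant | Direct 0.05 | Bonferroni only | Planned route |
|---|---|---|---|---|---|---|
| 0.6 | 0 | 0.6 | 70% | 55% | 38% | 29% |
| 0.6 | 0.3 worse | 0.6 | 56% | 55% | 38% | 25% |
| 0.6 | 0.3 better | 0.6 | 93% | 55% | 37% | 35% |
| 0.6 | 0.6 better | 0.6 | over 99% | 55% | 38% | 38% |
| 0.6 | 0.3 better | 0.3 | 70% | 56% | 38% | 30% |
| 0.5 | 0.25 better | 0.5 | 68% | 41% | 25% | 20% |
| 0.8 | 0.25 better | 0.5 | 96% | 79% | 65% | 63% |

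The last two columns separate the two sources of loss. When the device beats control by 0.3 to 0.6 SD at correlation 0.6, the precondition costs 0 to 2 points and the rest is Bonferroni. At correlation 0.3 it costs up to 8 points (38% to 30%), and with no device effect at correlation 0.6 about 9 (38% to 29%).

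**Step 4: range over a grid.** Crossing device effect 0, 0.25, 0.5, 0.8, correlation 0.3, 0.5, 0.7, and an effect sustained, at T1 only, or halved at T2 (6,000 runs each):

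- d = 0.5: planned route 0.12 to 0.26 against about 0.42 direct, keeping about 28% to 63%.
- d = 0.8: 0.43 to 0.66 against about 0.80 direct, keeping about 54% to 82%.
- With a 9-test family, roughly 20% to 37% is kept at d = 0.5 and 44% to 63% at d = 0.8.

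The low ends come from no device effect and correlation 0.3, and move by a few points between runs.

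**Step 5: device effect but no LINE effect.** With device 0.8 SD better than control, LINE effect zero and correlation 0.6, the interaction is significant about 93% of the time. The later Arm 1 versus Arm 2 test at T1 is falsely positive only about 1.5% of the time.

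**Step 6: no effects anywhere.** The planned route declares this contrast at T1 in about 0.2% to 0.3% of trials, against a per-comparison level of 0.05/3 = 1.67%.

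**The case against.** An omnibus test followed by Bonferroni is a familiar sequence that guards against false positives. Section 1 does not ask only about LINE: its opening aim is broader and a no-intervention arm is randomized, so a three-group analysis with all pairs has a rationale. The post-hoc step, when reached, includes Arm 1 versus Arm 2. All of that stands, and it limits the point in four ways.

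- A reader might infer that the plan roughly halves power as a rule. The documents give nothing from which to derive this. It is about right for d near 0.5 with a small device effect, but at d = 0.8 the loss can be about one fifth.
- A reader might infer a double penalty in every case. When the device works and visits are well correlated, the interaction condition costs almost nothing; the loss is ordinary Bonferroni.
- A reader might infer that a device-only effect would be reported as success for LINE. Nothing in the plan says so, and Step 5 shows that the post-hoc step would rarely support such a claim. The narrower point stands: the main analysis can be positive without bearing on LINE.
- Counting T1 alone understates the plan's chances, since it tests every visit. In the first row of the Step 3 table it declares the contrast at T1 or T2 in about 40% of trials. That gain exists because no deciding visit is named.

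Baseline adjustment would raise power further (from about 55% to 74% in that same scenario for the direct test), but that is a separate choice and no credit to removing the interaction condition.

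The false-positive defence does not require this route. One primary contrast at full alpha, with the remaining pairs tested by Holm only after it succeeds, also controls error across the three pairs. Dropping adjustment altogether would not: three unadjusted tests give about 1 − 0.95³ = 0.14 under independence.

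**Conclusion.** The point holds as one of alignment and efficiency, and should be fixed. The comparison that Section 1 singles out is reached only through a test that does not address it, at a level and visit left open. Neither the precondition nor the smaller alpha can raise power for the same contrast, so the direction of the cost is certain. Its size is not: about one fifth to seven tenths of the direct test's power over d = 0.5 to 0.8, under three-pair Bonferroni at T1, SD 1, no dropout and correlations of 0.3 to 0.7. The precondition adds materially when the device effect is small or the correlation is low; otherwise most of the loss is Bonferroni.

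A reader might go further and call the plan invalid. The documents do not support that: on this contrast it is conservative. Nor would the fix make the trial well powered, since even the direct test has only about 42% power at d = 0.5.

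**What to change.** In Section 6:

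1. Delete the condition that makes group comparisons depend on a significant interaction.
2. Pre-specify Arm 1 minus Arm 2 at one named visit (for example T1, post-intervention) as the primary contrast, on the primary outcome once Sections 5 and 6 are reconciled on what that is. Test it directly at two-sided 0.05 and report its 95% CI.
3. Test Arm 1 versus Arm 3 and Arm 2 versus Arm 3 by Holm only if the primary contrast is significant; otherwise report them with CIs as secondary.
4. Treat T2 as a maintenance analysis and report the interaction descriptively.
5. State the assumed effect, SD and correlation, and the resulting power for this contrast.

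The cost is SAP wording. The downside is small: the comparisons with control become secondary, and formal testing of them depends on the LINE result.

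### Post-hoc rule: Holm is never less powerful than single-step Bonferroni for the same family, and group tests at T0 answer no trial question (cheap improvement, minor)

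*Combined protocol and SAP*

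**What the plan says.** Section 6 (Post-hoc Testing) applies one rule, conditional on the omnibus test: "If a significant interaction is found", then "Bonferroni-adjusted post-hoc tests will be conducted to identify specific differences between groups at each time point". The omnibus test is the "Group-by-Time interaction effect on total sedentary time", and "The alpha level is set at 0.05".

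Section 5 lists three time points, the first of them before the intervention: "Data are collected at Baseline (T0), Post-intervention (T1, 1 month), and Follow-up (T2, 2 months"). Section 2 gives the size: "A total of 75 participants are randomly assigned to one of three groups in a 1:1:1 ratio", that is 25 per arm.

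Section 1 singles out one contrast, whether LINE support "provides incremental benefits compared to using a wearable device alone". That is Arm 1 vs Arm 2.

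The plan does not say whether the Bonferroni family is the three pairs at one visit or all nine pair-by-visit tests. It names no primary visit, and gives no effect size, SD, correlation, dropout or power.

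**The concern.** Two features of the rule look wasteful.

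First, single-step Bonferroni holds every pair to the strictest threshold. Holm starts at that threshold and relaxes it after each rejection. It therefore rejects everything Bonferroni rejects, sometimes more, with the same strong family-wise control under the same assumptions. Arm 1 vs Arm 2 could benefit if it is smaller than Arm 1 vs control, because the larger contrast would tend to be rejected first.

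Second, a test between randomised groups on data taken before the intervention cannot show a treatment effect. It either takes a share of the correction or adds a route to a chance finding, depending on how the family is defined.

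At stake is some power on the question the trial names, with 25 per arm, and a cleaner list of claims.

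**Working it through.** **Inputs from the documents.** 75 participants at 1:1:1, so n = 25 per arm; alpha 0.05 (two-sided assumed); three arms, so three pairs per visit; three visits. There is no power figure in the plan to reproduce.

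**Assumed inputs.** Effects in SD units, no dropout, pooled-variance t tests with 72 df. Because effects are standardised, the results do not depend on which activity measure is analysed.

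**Step 1. Single-step power for Arm 1 vs Arm 2.** Noncentral t, noncentrality d × √(n/2) = d × √12.5 = 3.536d.

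| d | 0.05 | 0.05/2 | 0.05/3 | 0.05/6 | 0.05/9 |
|---|---|---|---|---|---|
| 0.5 | 41.5% | 30.7% | 25.4% | 18.1% | 14.6% |
| 0.8 | 79.7% | 70.5% | 64.7% | 54.8% | 49.2% |

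**Step 2. Ceiling on the Holm gain, three tests.** The gain cannot exceed power at 0.05 minus power at 0.05/3: 41.5 − 25.4 = 16.1 points at d = 0.5, and 79.7 − 64.7 = 15.0 at d = 0.8. If only one other pair can be rejected first, the ceiling is 30.7 − 25.4 = 5.3 and 70.5 − 64.7 = 5.8 points.

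**Step 3. Simulated Holm gain, three tests at T1, unadjusted** (SD 1, correlation 0.5, 12,000 trials per scenario, interaction condition not applied). Columns are the Arm 2 vs control effect.

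| Arm 1 vs Arm 2 | 0 | 0.3 | 0.5 | 0.8 |
|---|---|---|---|---|
| 0.5 SD | +1.8 | +4.5 | +7.8 | +11.8 |
| 0.8 SD | +3.4 | +6.5 | +9.2 | +13.6 |

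Over Arm 1 vs Arm 2 effects of 0.2–1.2 SD and device effects of 0–0.8 SD, the range is +0.3 to +15.2 points. Of the 28 scenarios, 21 gain less than 7 points. With no device effect the range is +0.3 to +3.4. Requiring a significant interaction first shrinks gains where effects are small: for 0.5 SD with no device effect, from 1.8 to 0.9 points.

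**Step 4. Larger effects with baseline adjustment.** If the comparisons were adjusted for baseline with r = 0.6, the residual SD would be √(1 − 0.36) = 0.8. Power for Arm 1 vs Arm 2, three tests at one visit, 100,000 trials per scenario:

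| Arm 1 / Arm 2 vs control | Bonferroni | Holm | Gain | Shaffer |
|---|---|---|---|---|
| 1.0 / 0.5 SD | 41.0% | 52.8% | 11.8 | 58.6% |
| 1.0 / 0.4 SD | 58.0% | 67.7% | 9.7 | 73.9% |
| 0.9 / 0.3 SD | 58.1% | 65.9% | 7.8 | 73.2% |
| 0.8 / 0.4 SD | 25.2% | 32.5% | 7.3 | 40.2% |

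Section 6 states no baseline covariate. Unadjusted, the same four scenarios gain about 4 to 7.5 points. Shaffer's version uses the fact that, with three arms, once one pair differs at most one of the other two equalities can hold, so both can be tested at 0.05.

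**Step 5. What T0 tests cost.**

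- *One family of nine.* Dropping T0 moves the Bonferroni threshold from 0.05/9 to 0.05/6. Power rises from 14.6% to 18.1% at d = 0.5 and from 49.2% to 54.8% at d = 0.8.
- *Three tests per visit.* T1 and T2 thresholds stay at 0.05/3, so there is no power cost. The cost is extra false pairwise claims. Simulated with the interaction condition and correlation 0.6, the chance of at least one, with and without T0 tests, is 8.9% and 5.7% if Arm 1 differs at T1 only, by 1.2 SD; 4.0% and 1.8% if Arm 1 differs by 0.5 SD at T1 and T2; and 1.7% and 1.2% if nothing differs.

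**Step 6. Holm over six tests (T1 and T2).** Compared with within-visit Bonferroni, in the four Step 4 scenarios: 41.1% → 42.8%, 57.9% → 58.7%, 58.1% → 57.0%, 25.7% → 24.3%. At 0.5/0.1 SD: 25.6% → 20.5%. Compared with six-test Bonferroni the gain is about 0 to 12 points in scenarios of this kind, and 0.2 to 17.5 over the Step 3 grid.

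**The case against.** The strongest case for leaving the rule alone is that Bonferroni is valid and conservative and has matching simultaneous confidence intervals, which Holm lacks. Any power gain rests on effect sizes the plan never states and may be a point or two. All of that stands. It makes this an efficiency point and not an error, and it is why the rating is minor.

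Three stronger readings are tempting and are not supported.

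- A reader might infer that the plan loses 7 to 12 points of power on the LINE contrast. That range needs Arm 1 at 0.8–1.0 SD better than control and a baseline adjustment that Section 6 does not state.
- A reader might infer that T0 tests take alpha from T1 and T2. They do so only in a nine-test family, and the plan does not say it uses one. The 7-to-12-point range belongs to the three-test family, where T0 costs no power, so the two losses cannot be added. In a nine-test family the Holm gain reached 7 points in only 1 of the 28 scenarios (7.7).
- A reader might infer that Holm over T1 and T2 together improves on whatever the plan does now. Against within-visit Bonferroni it gives similar or lower power in the Step 6 scenarios. It is ahead only where both effects are large (Arm 1 vs Arm 2 and the device effect both 0.8 SD: 64.4% → 72.2%).

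It is also fair to say that the 8.9% false-claim figure is close to a worst case, because so large an effect makes a significant interaction almost certain, and that a chance difference at T0 is not itself a treatment claim. What survives is that T0 group tests have no inferential use, and that for a fixed family Holm costs no error control.

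**Conclusion.** The point holds as a cheap improvement of minor severity. Two parts do not depend on assumptions: for any fixed family Holm dominates single-step Bonferroni on power at equal family-wise error, and under randomisation a pre-intervention group difference is chance.

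The size does depend on assumptions. The gain is largest when the device works by itself and LINE adds to it, and close to nothing when the device alone does little. It should be quoted only as a range with its scenarios.

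The undefined family matters as much as the choice of procedure. Three separate families at 0.05 could reach 1 − 0.95³ = 14.3% family-wise error if independent, and T1 and T2 alone 1 − 0.95² = 9.75%, both before the interaction condition is taken into account.

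**What to change.** Replace the post-hoc sentence in Section 6 with text such as:

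*Groups will not be compared by test at T0. The three pairwise group comparisons at T1 form the primary post-hoc family and will be tested with Holm's step-down procedure. T2 comparisons will be reported with estimates and confidence intervals.*

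With exactly three arms, Shaffer's version may be named instead: the smallest p-value at 0.05/3 and, if that rejects, the remaining two at 0.05.

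If T1 and T2 must both be confirmatory, use Holm over the six tests and say why. The benefit is error control across both visits; it should not be presented as a power gain over within-visit Bonferroni.

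**Cost.** A short SAP edit, made before the data are analysed, and a few threshold comparisons applied by hand to the SPSS p-values. No data, visits or participants change. There are two real downsides. T2 becomes descriptive under the main option. Holm also has no simple matching simultaneous confidence intervals, so intervals would be unadjusted or Bonferroni, and the SAP should say which.

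### Section 6 pre-specifies no estimate or confidence interval for LINE plus device versus device alone, and reaches that comparison only after a significant interaction

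*Combined protocol and SAP*

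**What the plan says.** Section 1 (Introduction and Objectives) says that the study specifically investigates "whether motivational support via social media (LINE) provides incremental benefits compared to using a wearable device alone". In the design of Section 2 that is Arm 1 against Arm 2.

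Section 6 (Statistical Analysis Plan) contains four elements:

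- baseline characteristics as means with SD, or frequencies;
- a 3 × 3 mixed ANOVA on total sedentary time, giving Group, Time and Group-by-Time effects;
- a conditional second step: "If a significant interaction is found, Bonferroni-adjusted post-hoc tests will be conducted";
- a significance level: "The alpha level is set at 0.05".

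The purpose of the second step is described as follows: "Bonferroni-adjusted post-hoc tests will be conducted to identify specific differences between groups at each time point". Section 6 mentions no mean difference, effect size, confidence interval or smallest worthwhile difference for any pair of arms. The only descriptive summaries it plans are at baseline.

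**The concern.** An incremental benefit has a size, and the plan does not commit to estimating it. The ANOVA interaction is an omnibus test over three arms and three times. It does not isolate Arm 1 versus Arm 2, yet it decides whether that comparison is made.

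Two consequences follow. If the interaction is not significant, no Arm 1 versus Arm 2 result is planned, so readers cannot tell whether LINE has no useful effect or the trial had too little information to show one. If the LINE difference is reported only when its own test is also significant, the published figure comes from a selected set of results, and in a small trial these are the large ones.

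**Working it through.** **Inputs from the documents.** Section 2: "A total of 75 participants are randomly assigned to one of three groups in a 1:1:1 ratio", so 75/3 = 25 per arm. Section 6: alpha 0.05 (two-sided assumed), with pairwise tests only after a significant interaction.

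**Not in the documents.** Outcome SD, expected effect, power, dropout, within-person correlation, smallest worthwhile difference, and whether Bonferroni covers 3 comparisons per time point or all 9. There is thus no stated calculation to reproduce. Results below are in SD units, with no dropout.

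**Step 1: precision of Arm 1 minus Arm 2 at one time point.** Half-width = t × √(2/25) = t × 0.283.

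- 95%, two arms only (48 df): 2.011 × 0.283 = 0.569 SD.
- 95%, variance pooled over three arms (72 df): 1.993 × 0.283 = 0.564 SD.
- Bonferroni over 3 (72 df): 2.451 × 0.283 = 0.693 SD. Over 9: 0.809 SD.
- Adjusted for a baseline value correlating 0.6 (not planned; 47 df): 2.012 × √(0.08 × 0.64) = 0.455 SD.

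An observed difference of zero is therefore compatible with a benefit of up to about 0.57 SD, and the plan does not commit to showing that.

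**Step 2: what a declared difference must look like.** With Bonferroni over 3, the observed difference must exceed about 0.69 SD to be significant. If the true effect is well below that, nearly every declared estimate lies above the truth.

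**Step 3: the written sequence, simulated.** 20,000 trials per scenario with 25 per arm. The interaction is tested at 0.05 on F(4, 144), then Arm 1 versus Arm 2 at T1 with Bonferroni over 3. Assumptions: the LINE effect is equal at T1 and T2; device-only versus control is 0, 0.3 or 0.5 SD; the common within-person correlation is 0.5 or 0.7. Ranges run over these six combinations. The last two columns are for declared results in LINE's favour.

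| True LINE effect (SD) | Interaction not significant | LINE difference declared at T1 | Mean declared estimate (SD) | Ratio to truth |
|---|---|---|---|---|
| 0.2 | 14–90% | 1–4% | 0.79–0.81 | 3.9–4.0 |
| 0.3 | 6–83% | 3–8% | 0.80–0.83 | 2.7–2.8 |
| 0.5 | 1–58% | 14–25% | 0.85–0.87 | 1.7 |
| 0.8 | 0–14% | 58–65% | 0.96–0.97 | 1.2 |
| 1.0 | 0–3% | 84–86% | 1.07–1.08 | 1.07–1.08 |

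A different correlation pattern (0.6 between T0 and each follow-up, 0.7 between T1 and T2), with a device effect of 0.3 SD and a true LINE effect of 0.3 SD, agrees. In 42% of trials the LINE comparison is never reached, 6% declare it at T1, and the mean declared estimate is 0.81 SD, or 0.81/0.3 = 2.7 times the truth. Declaring it at either follow-up would be more frequent than at T1 alone.

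**Step 4: where the exaggeration comes from.** In that last scenario the ratio is 1.09 among all trials that pass the interaction step, 2.68 for Bonferroni-significant results with no interaction step, and about 2.7 with both. An unadjusted test at 0.05 with no interaction step still gives 2.36. The source is selection on the pairwise test at 25 per arm. The interaction step adds almost nothing to it; its cost is the unreported comparison.

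**The case against.** The strongest reply is that much of this is read from silence. Section 6 is short and does not list reported outputs. It does not forbid mean differences, and identifying differences is compatible with giving their size. That stands: a reader might infer that the plan can deliver only significance verdicts, and the text does not support this. What it supports is that no estimate is pre-specified and that the comparison depends on the interaction. The second of these is a written rule, not a gap.

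A reader might also infer that any positive LINE result would be overstated. The documents give no true effect, and at about 1 SD the inflation is under 1.1. Nor does a missing interval cause the inflation. It comes from small arms combined with selection on significance, and adding an interval would not move the point estimate in a given significant trial. The interval would show the imprecision, and unconditional reporting would remove the selection across possible results.

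It would also go too far to say that the investigators will report a null result as LINE adding nothing. Section 6 has no interpretation rule in either direction.

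Finally, a rule for concluding no benefit would seldom be met. With a half-width of 0.46 to 0.57 SD, an observed difference of zero would meet it only if the margin exceeded roughly half an SD. That is true, and it is a limit of the sample size that the report should show.

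**Conclusion.** The point holds in limited form. Followed as written, Section 6 can leave the specific question of Section 1 with no planned numerical answer, and it commits to no interval that would show the roughly ±0.57 SD of uncertainty at 25 per arm. That rests on the text and on simple arithmetic, assuming equal variances and no dropout; with 20 per arm the half-width would be about 0.63 SD.

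The exaggeration is conditional. It applies if the comparison is reported only when significant, and its size depends on an unknown true effect: substantial at 0.5 SD or below, modest at 0.8, negligible from about 1.0. The factors also assume Bonferroni over 3 and the correlations used above.

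The change should be made, since it alters what the trial can conclude even if the sample size stays at 75.

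**What to change.** Add to Section 6:

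1. The mean differences Arm 1 minus Arm 2, Arm 1 minus Arm 3 and Arm 2 minus Arm 3 at T1 and T2 will be reported with 95% confidence intervals for each primary measure (steps per day and sedentary breaks), and for total sedentary time if it stays in the analysis, whatever the result of the interaction or any other test.
2. A non-significant result will not be read as no incremental benefit unless the confidence interval for Arm 1 minus Arm 2 excludes, in the beneficial direction, a smallest worthwhile difference that the sponsor fixes before analysis. Otherwise it will be reported as inconclusive.

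The direction must be set for each outcome. Benefit is a higher value for steps and sedentary breaks, so the upper limit must fall below the margin. Benefit is a lower value for total sedentary time, the only outcome that Section 6 names for the ANOVA, so there the lower limit must lie above minus the margin.

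The cost is SAP wording and agreement on the margin; no further participants or data are needed. The downside is that, at this precision, most null results will have to be reported as inconclusive.

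### The only planned test of device plus support against device alone compares unadjusted group means; adjusting it for the baseline already collected would gain precision at almost no cost

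*Combined protocol and SAP*

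**What the plan says.** Section 2 (Study Design and Setting) gives the size and allocation: "A total of 75 participants are randomly assigned to one of three groups in a 1:1:1 ratio". Section 1 (Introduction and Objectives) singles out one comparison, whether LINE support adds anything to the device alone, which is Arm 1 against Arm 2. Section 5 (Outcome Measures) words the primary outcome as a change, "Primary Outcome: Change in Physical Activity", and schedules assessments at baseline (T0), one month (T1) and two months (T2).

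Section 6 (Statistical Analysis Plan) makes the main analysis a mixed ANOVA with three groups and three time points, so T0 is one level of Time. The follow-up step is conditional: "If a significant interaction is found, Bonferroni-adjusted post-hoc tests will be conducted", and its purpose is "to identify specific differences between groups at each time point". On significance it says only "The alpha level is set at 0.05". Neither the main analysis nor the post-hoc step mentions a baseline covariate, a change contrast or a baseline-constrained model. The set of tests over which Bonferroni is applied is not stated.

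**The concern.** The interaction has four degrees of freedom and covers all three arms. It can be significant merely because both device arms depart from control, so it does not isolate Arm 1 against Arm 2. That question is left to the post-hoc pairwise tests, which on a plain reading compare raw group means at one visit at a time.

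Three things follow.

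- With 25 per arm, a raw comparison leaves unused the part of the between-person variation that T0 explains.
- A chance T0 difference between Arms 1 and 2 passes, in proportion to the correlation, into the T1 and T2 contrasts.
- Each time point includes T0, where any difference between randomised groups is chance, so those three tests answer no question.

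At stake is how well a small trial can answer the question it was set up for.

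**Working it through.** **Inputs from the documents.** 75 participants at 1:1:1 gives 75/3 = 25 per arm; alpha is 0.05; there are three visits. The plan gives no effect size, SD, power or correlation, so there is no power figure of its own to reproduce.

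**Assumptions.** Two-sided tests; correlation rho between T0 and follow-up of 0.3 to 0.7; effects of 0.6 SD (power) and 0.8 SD (imbalance check); no dropout.

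**Precision.** In SD units, the SE of a raw pairwise difference at one visit is sqrt(2/25) = 0.283. Adjusted for T0 it is sqrt((1 - rho²) × 2/25). The SE factor is sqrt(1 - rho²), and the equivalent raw arm size is 25/(1 - rho²). Power is for 0.6 SD at 0.05/3 = 0.0167, from the noncentral t distribution with 48 df, ignoring the interaction step.

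| rho | SE | SE factor | Equivalent n per arm | Power |
|---|---|---|---|---|
| raw | 0.283 | 1 | 25 | 37% |
| 0.3 | 0.270 | 0.95 | 27.5 | 41% |
| 0.5 | 0.245 | 0.87 | 33 | 49% |
| 0.6 | 0.226 | 0.80 | 39 | 57% |
| 0.7 | 0.202 | 0.71 | 49 | 69% |

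**Chance imbalance.** The T0 difference between two given arms has SD 0.283, so it exceeds 0.5 SD with probability 2 × (1 - Φ(0.5/0.283)) = 7.7%. Given a T0 difference of 0.5 SD and no true Arm 1 vs Arm 2 difference, the raw T1 contrast has mean 0.5 × rho and the adjusted SE as its spread. The raw test rejects beyond 2.394 × 0.283 = 0.677. At rho 0.5 the upper tail is 1 - Φ((0.677 - 0.25)/0.245) = 0.041. The same calculation, both tails, gives 0.027 at rho 0.3 and 0.053 at rho 0.7, against a nominal 0.0167.

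**With the interaction step included.** Trials were simulated with 25 per arm and equal correlation between visits, testing at 0.05/3.

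- *No effect in any arm.* Among trials with a T0 difference above 0.5 SD between the two arms, a significant interaction followed by a false raw T1 result occurs in about 0.7% (rho 0.5) and 1.0% (rho 0.7), below nominal.
- *Both device arms gain 0.8 SD at T1 and T2.* The interaction is significant in 86% (rho 0.5) and 98% (rho 0.7) of trials. Among those with the same T0 imbalance, a false raw Arm 1 vs Arm 2 result at T1 occurs in about 6% and 12%. A smaller run of 20,000 trials, of which only about 1,500 have such an imbalance, gave 4.8% and 10.7%. The baseline-adjusted contrast stays at about the nominal 1.7% or below.
- *All randomisations, no interaction step, no effect.* The raw test's error per pair is 0.018 (rho 0.5) and 0.017 (rho 0.7), so it is nominal.

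**T0 tests.** Three pairs at three visits make nine tests, 0.05/9 = 0.0056. Without T0 there are six, 0.05/6 = 0.0083. If Bonferroni runs over the three pairs within each visit, the threshold is 0.0167 either way.

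**The case against.** The strongest reply is that the plan does not ignore baseline. The interaction is a test of change, a stable T0 difference cancels out of it, and no post-hoc test is run without it. This stands, and the simulation bears it out: when no arm has an effect, the step holds false findings below nominal even under marked imbalance. It does not protect Arm 1 against Arm 2 once a shared device effect has made the interaction significant.

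A reader might infer that the planned tests are biased or have inflated type I error. The documents do not support that. Allocation is random, and over all randomisations the raw test keeps its level; the harm is conditional on the imbalance that happens to occur.

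A reader might also infer that testing at T0 certainly costs alpha. It does so only if the Bonferroni family spans visits, which the SAP does not say.

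The size of the gain is also open. At rho 0.3 it is small, four points of power, and the documents give no figure for choosing a value.

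Finally, the word change in the primary outcome refers to steps and sedentary breaks, while the SAP's model is for total sedentary time. That mismatch is a separate matter. The argument here does not depend on it, because it applies to any outcome measured at T0.

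**Conclusion.** The point holds as one of efficiency, with a limited secondary point about imbalance. The one comparison that answers the trial's specific question is planned on raw means although T0 is collected. Adjustment would be worth between about 2.5 and 24 extra participants per arm (27.5 - 25 to 49 - 25) over assumed correlations of 0.3 to 0.7, or 4 to 32 points of power for 0.6 SD at 0.05/3, ignoring the interaction step.

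The imbalance harm arises in the roughly 8% of trials with a T0 difference above 0.5 SD between the two arms, and then only if a device effect has made the interaction significant. The 6% and 12% figures rest on an assumed 0.8 SD gain in both device arms and correlations of 0.5 and 0.7.

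The tests at T0 should go because they are uninformative; a multiplicity penalty from them cannot be asserted. The planned tests are valid on average, so this is a recommended improvement and not an error that invalidates the analysis.

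**What to change.** Keep the Group-by-Time interaction from the mixed ANOVA as the omnibus test, so that the link between the two models is explicit, and replace the post-hoc sentence in Section 6 with:

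> If the Group-by-Time interaction is significant, pairwise group contrasts at T1 and T2 will be estimated from a model with the T0 value of the same outcome as covariate, Bonferroni-adjusted over the six contrasts (three pairs at two visits); T0 will be summarised descriptively and not tested between groups.

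A plain change score is not an adequate substitute. Its SE, sqrt(2(1 - rho) × 2/25), is 0.335 at rho 0.3, worse than raw (0.283), and only equals raw at rho 0.5.

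The change needs no new data. It costs one degree of freedom and a stated rule for participants with a missing T0 value. The sponsor should also choose the family knowingly. At 0.05/6 the adjusted power for 0.6 SD, by the same formula, is 31%, 39%, 47% and 59% at rho 0.3, 0.5, 0.6 and 0.7, against 28% raw. If the present intention is correction within each visit (37% raw at 0.05/3), moving to six contrasts outweighs the gain from adjustment at rho 0.3 and takes most of it at rho 0.5.
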